Randomly selected MdDS patient volunteers will be treated with the velocity storage habituation protocol (Group 1, Aim 1). Another group of randomly selected patients of Group 2 will be treated with readaptation of VOR. Before and after the treatment, the severity of the objective and subjective symptoms will be assessed. Indices of postural stability (Method 1) and time constant of velocity storage (Method 2) will be obtained as objective measures. Treatment will take place over four days. The severity of subjective symptoms will be assessed by a self-reported scale of 0-10, where 0 is no symptom, and 10 is the most difficult sensation of that symptom that the patient can imagine. Among these symptoms are brain fog, head pressure, the fullness of the ear, heavy head, headache, nausea, blurry vision, fatigue, sensitivity to fluorescent lights, scrolling of computer screen, sensitivity to noise, walking on a trampoline, the sensation of

| Page

gravitational pull-up or down. The visual disturbance will be determined by the Visual Vertigo Analogue Scale and Situational Vertigo Questionnaire. Physical, emotional, and functional aspects of disability related to MdDS will be obtained by Dizziness Handicap Inventory (DHI). The patient will undergo follow-up testing for objective and subjective symptoms at 2 weeks, 1 month, 3 months, and 6 months after the treatment.

Treatment will be considered effective if objective and subjective symptoms are improved at least 50%. The effectiveness of the two treatments would be compared immediately after treatment and up to one year of follow-up phone calls.

Description of Procedures Being Performed

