Determining parameters of head motion: The patient assessed will be asked to stand on the Wii board for one min. Some patients experience only internal sensations of rocking. For this reason, a wireless 3D accelerometer will be attached to their wrist. The patient will be asked to move the hand to imitate the internal sensation of motion. Data on body deviations about the center of mass or wrist motion will be recorded with a laptop computer at 1kHz. Traces are visually examined. If oscillations larger than ± 10 mm are observed, the frequency of oscillation is determined by fast Fourier transforms. If the body (or internal sensation) is rocking (Forward-back motion), then the head would be rolled during treatment. If the body is swaying, then the head will be pitched.

The first treatment will last 1 min. If improvement is reported, then treatment will be repeated for 1-2 min. We will also test if lower frequencies of head oscillation are effective. The typical set of treatments at lower frequencies includes oscillation at 0.1 Hz for 3 min and at 0.05 Hz for 5 min. The amplitude of head oscillation would be about $\pm 20^\circ$.

Description of the Source Records that Will Be Used to Collect Data About Subjects

Objective measure description:

Method 1: Determining postural stability: Static posturography would be obtained with a specifically designed program for a Wii board. The displacement of the center of pressure (COP) over a 1 min period will be measured, and the root means square (RMS) of the postural displacement would be computed (30) to compare the postural stability before and after the treatment. The total trajectory length (maximum excursion) of the COP deviation will be computed over 20 seconds.

Postural stability would be obtained in different conditions:

- 1) subject will have eye open feet 30 cm apart,
- 2) subject will be placed under strong fluorescent light and feet open,
- 3) subject will have an eye open under non-fluorescent light on,
- 4) subject will be tested with eye closed,
- 5) subject will be tested with eye open in a small closet (0.9×0.6 m) with extreme dim light,
- 6) subject will be assessed facing crowded shelves and in a narrow engineering room facing crowded shelves (5×0.91 m).

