Body bobbing would be measured by an accelerometer attached to the arm wrist. The patient would be asked to move their wrist up-down to imitate the internal sensation of bobbing. The presence of gravitational pull in sideways, forward or backward directions will be objectively measured with static posturography.

Method 2: Determining Time constant of velocity storage: Subject sits in a standard Barany chair in darkness. This device is commonly used for Vestibular Nystagmography (VNG) testing in clinics all over the world and at Neurology Department at Mount Sinai over the last 30 years. The time constant (Tc) will be determined from rotations at a constant velocity of $60^\circ/\text{s}$ ($200^\circ/\text{s}^2$) in clockwise and counterclockwise directions in darkness. After 60 s, when the per-rotatory VOR has decayed, a laser spot at eye level rotating with the subjects for 10 s will be used to suppress any residual VOR response. After the laser light is turned off, the chair will stop with the same acceleration rate to produce a post-rotatory VOR. 60 s later; the laser light will be displayed to suppress the residual VOR again. Rotatory and post rotatory nystagmus will be recorded. During the test, subjects will perform mental arithmetic, such as multiplication or division problems, arouse their alertness. Movements of the right eye will be recorded with a Video Oculography recording

| Page

system (VOG, ISCAN) at a rate of 60 frames/s. Data acquisition will be made through a LabView program at 600 Hz/s/channel. The data will then be transferred to the VMF data management software for further processing. Eye position data from the VOG will be digitally differentiated to obtain eye velocity. Quick phases will be removed, leaving slow phase eye velocity for analyses (Engelken and Stevens 1990). Slow phase velocity traces will be fitted with two Tc's fitting algorithm, where the first Tc is fixed to 5 s (copular Tc) and the second need to be determined (Tc of velocity storage). This algorithm is now embedded in our standard VNG testing protocol.

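### The bobbing measure listed as objective records a gesture the patient chooses to make, and the 50% success rule does not bar it from counting as objective improvement

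*Protocol*

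**What the plan says.** The Protocol, *Description of the Study Design*, names the objective measures: "Indices of postural stability (Method 1) and time constant of velocity storage (Method 2) will be obtained as objective measures". The same section sets the success rule: "Treatment will be considered effective if objective and subjective symptoms are improved at least 50" per cent. It does not say which objective measure decides.

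The details follow under "Objective measure description". Method 1 begins with static posturography on a Wii board. The root mean square (RMS) of centre-of-pressure displacement is computed "to compare the postural stability before and after the treatment", and several viewing conditions are listed. Still within Method 1, the text turns to bobbing: "Body bobbing would be measured by an accelerometer attached to the arm wrist". The next sentence explains where the signal comes from: "The patient would be asked to move their wrist up-down to imitate the internal sensation of bobbing". Method 2, the time constant of velocity storage, comes after that.

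A similar wrist recording appears earlier, under *Determining parameters of head motion*: "The patient will be asked to move the hand to imitate the internal sensation of motion". It belongs to the set-up of the readaptation treatment.

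**The concern.** An accelerometer looks like an objective instrument, but objectivity depends on what produces the signal. Posturography records how the body moves while the patient stands. The bobbing trace records how far and how fast the patient decides to move a wrist to show what is felt. A patient who believes the treatment has helped can show a smaller movement, just as the same patient can give a lower score on the 0-10 scale.

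Requiring objective as well as subjective improvement gives the success rule some protection against expectation. That matters here because patients very probably know which treatment they received. If an imitated movement can count as objective, the protection is lost for this symptom, and a report of objectively confirmed improvement in bobbing would claim more than was measured.

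**Working it through.** No arithmetic applies. The question is how a measure is classified, and the protocol attaches no figure to it. The check sets the relevant texts side by side.

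1. **Where the bobbing test is filed.** It lies under the objective-measure heading, after the posturography conditions and before Method 2. On the face of the document it is part of Method 1.

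2. **What produces the signal.** The patient imitates an internal sensation by hand. The recorded amplitude is the patient's choice, so the trace is patient-reported information captured by a device. The sentence that follows it assigns gravitational pull to static posturography, which records the body itself.

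3. **Whether the success rule excludes it.** *Description of the Study Design* refers to Method 1 as objective and requires objective improvement. It neither names the deciding measure nor excludes the wrist trace. As written, the trace can count.

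4. **Whether another Method 1 measure covers bobbing.** *Description of Data that Will Be Collected Including Long-Term Follow-Up* says centre-of-pressure oscillation is collected forward-back and side-to-side only. Vertical motion is not covered, so the wrist trace is the only listed Method 1 measure of bobbing. Bobbing is also one of the qualifying sensations in the inclusion criteria.

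5. **Whether the patient knows the treatment.** The protocol describes no masking. Under Aim 1 the chair rotates against a conflicting visual stimulus in 20-minute sessions. Under Aim 2 a researcher moves the head by hand during treatments of 1 to 5 minutes. *How Participants Will Be Identified* plans to contact previously treated patients, some of whom may recognise readaptation. Knowledge of treatment is therefore a strong inference, though not an explicit statement.

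6. **Whether the other wrist test is affected.** The internal-motion recording comes before the objective-measure heading, and its stated use is to choose the frequency and plane of head movement, for example "If the body (or internal sensation) is rocking (Forward-back motion), then the head would be rolled during treatment". No outcome use is given.

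Steps 1 to 3 show that a self-report can stand as objective improvement. Steps 4 and 5 show why this matters for bobbing. Step 6 limits the point to the bobbing trace.

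**The case against.** The strongest reply is that nothing actively puts the wrist trace into the success rule. The design section speaks of indices of postural stability, and an imitated wrist movement is hardly such an index. The protocol defines no RMS, percentage change or before-and-after comparison for it, although it does define a before-and-after comparison for posturography. The description of data to be collected lists eye movement and centre-of-pressure data but no wrist data. The choice of deciding measure may also be settled in a statistical analysis plan that is not at hand.

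Much of this stands, and it is why the point is minor. It does not remove the point. The protocol itself files the trace among the objective measures and itself states a rule that depends on that label. The misplacement is in this document, whatever is specified elsewhere.

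A reader might infer more than the text supports in two ways:

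- **That wrist imitation of internal rocking or swaying is also classed as objective.** It is not. It is described only as treatment set-up.
- **That in patients with bobbing or internal sensations both halves of the rule necessarily come from the patient's own report.** This is not established. Centre-of-pressure RMS and the time constant are planned with no exclusion for these patients, and neither is acted out by hand. The rule leaves open which measure decides, so the most that can be said is that the objective half can be met this way for bobbing.

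**Conclusion.** The concern holds in limited form, and its severity is minor. One measure that depends on the patient's own demonstration is listed as objective, and the success rule does not prevent it from serving as the objective component. The consequence is confined to bobbing.

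The effect on success rates cannot be computed. The protocol gives neither the share of patients whose main motion is bobbing, nor the spread of improvement on any measure, nor the way the trace would be scored. Any figure would have to be invented, and it would illustrate expectation bias in an open comparison generally rather than the effect of this classification.

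The conclusion rests on two readings: that the bobbing sentences belong to Method 1, as their position indicates, and that patients know their treatment, as the visible difference between procedures and the absence of any masking text suggest.

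**What to change.** Make two short edits to the Protocol.

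- **Objective measure description, Method 1:** move the imitated bobbing trace to the subjective measures and describe it as patient-reported.
- **Description of the Study Design:** state that this trace never counts towards the objective half of the 50% rule. That half uses only measures the patient does not act out, drawn from those the protocol already names as objective: the postural stability indices and the time constant.

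Restricting the objective half to posturography alone would go too far. It would drop the time constant, which the protocol names as objective, without giving a reason. It would also rely wholly on a measure that does not record vertical motion.

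The wording costs almost nothing. The real cost is that patients whose only motion is bobbing will have no direct objective measure of that symptom, so fewer patients can be called objectively improved. The report should say so and give the number of such patients in each group. The wrist recording used for treatment set-up needs no change on this account.

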Specific Aim 1: Assess the efficacy of MdDS treatment via habituation of velocity storage. It was previously demonstrated that the contribution of velocity storage to the VOR could be eliminated by a habituation protocol. Fifteen MT MdDS patients with no peripheral vestibular abnormalities (Group 1) will undergo this protocol over the period of four days. Objective and subjective symptoms will be assessed with a standardized test battery (**Methods 1**) before and after habituation.

Specific Aim 2: Further assess the efficacy of MdDS treatment via VOR readaptation and compare success rate with Group 1, which underwent the habituation protocol. Fifteen MT MdDS patients with no peripheral vestibular abnormalities (Group 2) will undergo the VOR readaptation protocol over the period of four days. Objective and subjective symptoms will be assessed with a standardized test battery before and after readaptation. Treatment effectiveness will be compared between the two groups immediately and 6 months after treatment.

Number of subjects

| Page

Subjects To Be Enrolled	60
-------------------------	----

Study Timelines

We planning to recruit all 60 patients by August 2022.

Duration Anticipated to Enroll All Study Subjects

18 months

Estimated Date for the Investigators to complete this study

Within 3-5 years

Setting of the Human Research

How Participants Will Be Identified

Vestibular Testing Center at Mount Sinai has treated 3-7 patients with MdDS on a weekly basis, receiving 3-15 applications for treatment per week. The treatment is advertised on web sites of Mount Sinai and Vestibular Testing Center (www.mdds.nyc). We anticipate reaching out to all previously treated MdDS patients who are part of the Vestibular Testing Center's clinical database to offer the study. The study treatment provider ([name], PI) will mail or email the letter discusses the study and the ability for the participant to 'opt out' of being contacted concerning the study.

How Research Will Be Introduced to Participants

Potential subjects will be interviewed over the telephone for confirmation and clarification of their MdDS symptoms. Once the participant potentially meets the entry criteria, they will be consented over the phone following the HRP 093 policy are scheduled for a screening visit or a screening telephone call.

How Participants Will Be Screened

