Aim 1: Velocity storage habituation protocol: The central vestibular (velocity storage) time constant will be habituated (reduced) by inducing cancellation of two velocity storage-mediated responses: optokinetic nystagmus (OKN) and the vestibulo-ocular reflex (VOR). The stimulus velocity and the frequency must be low to activate the response characteristics of velocity storage. Low-frequency rotation in darkness advances the phase of the slow phase eye velocity of the induced nystagmus. In normal subjects, the VOR during oscillation at 0.017 Hz has a phase advance of 32° relative to the stimulus and a gain of 0.68 on average. In contrast, the OKN induced by low-frequency optokinetic stimuli has no phase advancement in the slow phase eye velocity. Thus, to counteract the VOR by OKN, the optokinetic stimulus should be set to be 180° out of phase with the expected VOR. Across all subjects, we will use a gain of 0.68 and a phase advance of 30° to generate the optokinetic stimulus relative to the velocity of the chair in which the subject is seated. The optokinetic stimulus occupying the entire visual field is a powerful stimulus, and subjects will not be particularly attentive to the moving stripes to experience the visual motion. Chair velocities will be up to 40°/s. The conflict stimulus is expected to be overwhelming to the patients depending on the stimulus velocities. Subjects will be first tested with a 10°/s stimulus. If they feel uncomfortable, the chair velocity will be reduced to 5°/s or 2°/s and increased gradually. From previous studies, no complaints were reported when subjects were tested at low velocities (Dai et al., 2011). In our preliminary testing, MdDS patients began to show signs of symptom improvement when the peak velocity reached 30°/s. In total, three habituation sessions will be administered each day over the four-day period. Two consecutive sessions with identical stimulus parameters, each lasting 20 min, will be administered with a 10 min break. Then the third session will be administered with an increase in the chair velocity by up to 10°/s. If signs of motion sickness are reported by the subject (nausea, sweating) session will be terminated. Thus, some subjects may not be able to complete the entire 20 min of the intensified stimulus. Therefore, the subjects are expected to undergo 200-280 min of habituation over the 4-5 day period. Eye movements will not be recorded during the habituation training.

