Subjective measure description: Strength of subjective symptoms will be obtained with subjective self-score on a scale of 0-10, where 0 is no symptom, and 10 is the highest sensation of that symptom that the patient could imagine. Among these symptoms are brain fog, head pressure, the fullness of the ear, heavy head, headache, nausea, blurry vision, fatigue, sensitivity to fluorescent lights, scrolling of computer screen, sensitivity to smell, sensitivity to noise, walking on a trampoline, the sensation of gravitational pull-up or down. The Visual Vertigo Analogue Scale will determine the visual disturbance. Physical, emotional, and functional aspects of disability related to MdDS would be obtained by Dizziness Handicap Inventory (DHI).

Description of Data that Will Be Collected Including Long-Term Follow-Up

Prior to the treatment standard, a VNG test will be performed to determine any significant vestibular abnormality. That includes rotational and caloric tests. Patients with significant central abnormalities will be rejected from this study (see Recruitment method). If the patient has a VNG report done after the onset of MdDS, the only rotational test will be performed to obtain the time constant of VOR (velocity storage). The rotational test will be repeated at the end of the treatment (see Method 2 above). During the rotational test, horizontal and vertical components of eye position in response to chair rotation will be collected for 2 min. The test will be repeated 3 times for statistical purposes. Data in VMF-format will be collected and stored in a computer folder with the patient's ID number.

Prior to and during treatment, static posturography will be performed (Method 1). COP oscillation about X-(forward-back) any Y-axis (side-to-side) will be collected. Data in VMF-format will be collected and stored in a computer folder with the patient's ID number.

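### The Method 2 velocity-storage time constant is not identified once storage is eliminated, so complete habituation can be recorded as no change or a lengthening

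*Protocol*

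**What the plan says.** Method 2 (Determining Time constant of velocity storage) describes velocity steps of 60°/s "in clockwise and counterclockwise directions in darkness". Per-rotatory and post-rotatory responses of 60 s each are recorded. The analysis is then fixed: "Slow phase velocity traces will be fitted with two Tc's fitting algorithm, where the first Tc is fixed to 5 s", and "the second need to be determined (Tc of velocity storage"). The text adds that this algorithm is already part of the laboratory's standard VNG testing.

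Three other places bear on it:

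- Under Description of Procedures, the Aim 1 protocol states the intended effect of Group 1 treatment: the "time constant will be habituated (reduced").
- Specific Aim 1 goes further and says that earlier work showed "the contribution of velocity storage to the VOR could be eliminated by a habituation protocol".
- The section on data to be collected says "The rotational test will be repeated at the end of the treatment" and, of the rotational test, "The test will be repeated 3 times for statistical purposes".

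Description of the Study Design lists the time constant, with postural stability, as an objective measure.

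**The concern.** The estimator asks the data for the decay rate of a second component. That question has an answer before treatment, when the component is large and slow. If treatment removes the component, there is nothing left whose decay rate could be estimated, and the fitted constant is set by noise and by the limits of the search. If the component shrinks, or its constant moves close to 5 s while its size stays put, the answer becomes progressively less precise.

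The time constant is the trial's direct evidence that velocity storage was habituated, and the hypothesis is that habituation resolves MdDS symptoms. A patient whose storage has been abolished could be entered with a constant equal to or longer than baseline. That would distort the before-after change in Group 1, the comparison with Group 2, and any analysis linking habituation to symptom relief.

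**Working it through.** The protocol gives no precision figure for this measure, so there is nothing to reproduce.

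**Inputs from the protocol.** One constant is fixed at 5 s and each decay lasts 60 s. There are 2 directions × 2 responses (per- and post-rotatory) × 3 repeats = up to 12 decays per visit, on my reading. As a check on the baseline, the protocol gives a phase advance of 32° at 0.017 Hz in normal subjects. With T = 1/(2πf·tan φ), this is 1/(0.1068 × 0.6249) ≈ 15.0 s; at 30° it is 16.2 s.

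**Assumptions, not in the protocol.** Initial slow-phase velocity is 40°/s, noise SD is 1 to 5°/s, there are 2 or 4 independent values per second, and the baseline constant is 15 or 18 s.

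**Step 1: the algebra.** The model is y(t) = A·exp(−t/5) + B·exp(−t/T). Its sensitivity to T is B·(t/T²)·exp(−t/T). So SE(T) is proportional to (noise SD)/B. It grows without limit as B goes to 0, and at B = 0 the constant T is absent from the equation.

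**Step 2: standard errors.** Fisher information, noise SD 3, 2 values per second; pooling 12 decays divides the SE by √12 = 3.46.

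| A, B, T | SE, one trace (s) | SE, 12 traces (s) |
|---|---|---|
| 20, 20, 15 | 2.4 | 0.7 |
| 20, 20, 7.5 | 4.0 | 1.2 |
| 20, 20, 6 | 7.8 | 2.3 |
| 35, 5, 15 | 9.4 | 2.7 |
| 38, 2, 15 | 23.6 | 6.8 |

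**Step 3: simulation.** 4 values per second, noise SD 3, T searched over 5 to 60 s. Ranges are 5th to 95th percentiles.

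- Before treatment (20, 20, 18): one trace gives 15.5 to 21 s.
- Shortened to 9 s: pooled trace 7.9 to 10.0 s. To 8 s: pooled trace 6.8 to 9.2 s.
- Shortened to 6 s: 13 to 17% of single traces exceed 18 s, but the pooled trace gives 5.0 to 10.2 s with none above 18 s.
- Small storage component (36, 4, 12): about 30% of single traces exceed 18 s; pooled, 8.5 to 17.6 s with 3.5% above.
- Storage eliminated (40, 0): single and pooled fits both span 5 to 60 s. Between 31 and 45% of single traces exceed 18 s, at SD 3 and at half that noise, with or without non-negative amplitudes. The mean of 12 separate fits has a median of about 26 s (15 to 37), above the 18 s baseline.

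Widening the search to 0.5 to 100 s leaves the eliminated case spanning those limits too, with 33 to 37% of pooled fits above 15 s.

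**Step 4: the overall constant from the same traces.** A single-exponential fit gives 11.9 s before treatment (11.1 to 12.7). With storage eliminated the true value is 5 s. For dense sampling at interval d, SE = (SD/A)·√(8dT) = (3/40)·√(8 × 0.25 × 5) = 0.24 s, so one trace gives 5 ± 1.645 × 0.24, or 4.6 to 5.4 s. Area divided by initial velocity behaves alike: (20×5 + 20×18)/40 = 11.5 s before, ignoring the cut at 60 s, and (40×5)/40 = 5.0 s after.

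**The case against.** The strongest reply is that the trouble depends on a model the protocol does not spell out. In a coupled storage model the two amplitudes move with T: y = g0·exp(−t/5) + g1·[exp(−t/T) − exp(−t/5)]/(1/5 − 1/T). Here B = g1/(1/5 − 1/T), so at g1 = 4 it rises from 30 at T = 15 to 60 at T = 7.5. That growth offsets the similarity of the two curves. With g1 staying at 4 and noise SD 3, the SE per trace is 1.6 s at T = 15, 1.3 s at 7.5 and 1.3 s at 5.01. This stands: shortening alone need not do harm. It does not cover elimination. As g1 falls from 4 to 2, 1, 0.5 and 0.1, with T = 15, the SE goes 1.6, 3.1, 6.3, 12.6 and 63 s.

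Two stronger readings are tempting and are not supported. A reader might infer that the constant fails as soon as habituation shortens it. The pooled results for 8 and 9 s show otherwise, and the protocol elsewhere speaks of reduction rather than elimination. A reader might also infer that the measure fails in exactly the patients whom treatment helps. The success rule in Description of the Study Design is at least 50% improvement in objective and subjective symptoms. It does not require that storage vanish, nor say whether the time constant counts.

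It is also fair that handling of amplitudes and pooling of repeats may be settled in an analysis plan or laboratory procedure not shown. Their absence is not the point. The point is that the estimator the protocol does fix has no target at an effect the protocol itself names. Standard use in VNG testing does not show that the fit is valid after storage has been removed. Finally, the measure is one of several objective ones and is not named as primary, and the recordings are kept, so the harm is repairable.

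**Conclusion.** The point holds in a limited form. At elimination of storage the reported constant is unidentified. This follows from the algebra and needs no assumption about noise. Under the assumptions above, 31 to 45% of single traces would then show a constant above an 18 s baseline, and pooling 12 decays gives no protection. The error falls mainly on Group 1 at the end of treatment.

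Short of that limit this is a question of precision: slight for moderate shortening with pooled traces, and larger as the storage component becomes small, or as its constant nears 5 s if the amplitudes do not move with it. Its size there cannot be settled from the protocol, because noise, initial velocity and amplitude constraints are not stated. How many patients would reach elimination is also unknown. The documents do not support dropping the two-constant fit; it remains the measure that targets storage specifically.

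**What to change.** Add three sentences to Method 2:

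1. From the same recordings, compute the overall VOR time constant (single-exponential fit, or area under slow-phase velocity divided by initial velocity) before and after treatment in both groups. Use it as the habituation measure alongside the two-constant fit.
2. Fit the pooled traces of each visit instead of averaging separate fits. In the 6 s case pooling gives 5.0 to 10.2 s, against 6.7 to 17.8 s for the mean of 12 fits.
3. Where the second component is indistinguishable from zero or from the 5 s component, by a criterion set in advance, record the patient as having no detectable storage. Rely on the overall constant there, not on the fitted second constant.

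The cost is a wording change and one refit of recordings already planned, with no added testing. The downside is that the overall constant mixes cupula and storage. Its range is narrower (about 12 to 5 s here), and it is less comparable with the laboratory's earlier values, which is a reason to keep reporting both.
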